testing both of these interventions against a comparison group receiving the smoking cessation intervention with bibliotherapy support, we will move the field forward in identifying the most promising approaches to reducing postcessation weight gain.

Another novel feature of the proposed study is our target population. While previous studies have largely focused on women (16), we will have targeted recruitment of men, so that we recruit both men and women to this study, to facilitate the generalizability of our findings. In addition, men were found in previous research (32) to be more likely to relapse after weight gain. Furthermore, most previous studies of postcessation weight gain interventions failed to even report the race/ethnic composition of their sample (17), let alone focus on recruiting a diverse sample, as we plan to do. For these reasons, we expect our proposed interventions, if as effective as expected, will make a significant public health contribution to curtailing escalating obesity in this vulnerable population.

3. Study/ Project Population

In this study, we will determine whether two very promising methods of reducing postcessation weight gain, namely a weight stability intervention versus a weight loss intervention followed by a smoking cessation intervention, are efficacious for reducing postcessation weight gain. Given the negative health implications of weight gain after smoking cessation and the difficulty in reducing postcessation weight gain in previous interventions, **we propose the following:**

To randomize up to 400 smokers to 1 of 3 arms: a) a weight stability intervention prior to cessation (Group 1); b) a weight loss intervention prior to cessation (Group 2); or c) a self-guided weight management prior to cessation (Group 3) and to determine the efficacy of the interventions on preventing weight gain at 12 month follow-up. All 3 conditions receive a highly efficacious behavioral smoking cessation program and 6 months of varenicline pharmacotherapy (ChantixTM), the most efficacious medication for smoking cessation (21, 22). Since smoking cessation and body weight are confounded, smoking cessation status and duration of cessation will be examined as covariates.

Inclusion Criteria:

- Participants must be 18 years or older
- Participants must wish to quit smoking in the next 30 days
- Participants must have smoked 5 or more cigarettes a day for at least 1 year

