The biostatistician will randomize the participants to one of the three study conditions. Participants (n=400) will be randomly assigned in a ratio of 2 (Group 1, n=160): 2 (Group 2, n=160): 1 (Group 3, n=80). However; when less than 40 participants are recruited for a wave, the biostatistician will more evenly distribute the participants. Participants will be asked to complete another remote study visit for their randomization assignment and to meet their interventionist. Prior to this visit, participants will be mailed their study materials. After this visit, participants will be asked to weigh again on the BodyTrace scale.

Weight Management Interventions. Participants will complete their randomly assigned weight management intervention before initiating the smoking cessation intervention.

Weight Stability Condition (Group 1). Participants will be asked to keep their weight stable during the initial 8 weeks of the study.

Intervention Components:

- 1) Participants will receive **lesson materials** adapted from the Small Changes intervention (19).
- 2) As frequent weighing is a key component to this and most weight management programs (82), participants will be encouraged to engage in **daily weight self-monitoring** on the BodyTrace™ e-scale (<http://www.bodytrace.com/>), which they will be given at randomization. Each time a participant weighs, the e-scale will upload the weight automatically to a secure database, so that timely tailored feedback on weighing frequency/progress can be provided by the interventionist through email.
- 3) Participants will be provided with **Fit Bit activity trackers** to self-monitor their steps, consistent with the Small Changes intervention.
- 4) If subjects are randomized to Group 1, they will receive via mail a small reward valued less than two dollars, each week during the weight and smoking cessation sessions, then monthly during the booster

sessions, if they maintain their baseline weight or maintain a weight that is less than 1.4 kilograms above their baseline weight.

Weight Loss Condition (Group 2). Participants will be asked to achieve a weight loss goal of at least 5% of their baseline weight by week 8.

Intervention Components:

- 1) Participants will receive **tailored calorie and fat goals** based on their baseline weight (83).

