Behavioral Smoking Cessation Intervention. Participants in all conditions will get our evidence-based in-person 6 session group-based smoking cessation intervention (44, 45, 89). Participants will transition to the smoking cessation intervention at week 9; they will receive the smoking cessation intervention with the same group with whom they received the weight management intervention, in order to preserve group social support as well as reduce contamination concerns. First, we will prepare participants for the quitting process, including providing varenicline at the first session. We will guide them through setting a quit date, implementing smoking cessation "rituals" (e.g., getting rid of ashtrays), reducing the number of cigarettes per day, and what to expect when they quit (e.g., withdrawal symptoms). By anticipating these issues, participants are able to better cope with them when they do arise. The second phase is the actual quitting process and getting through the first several days of being a nonsmoker. Given that this is the most difficult phase for participants (and is when the most relapse occurs), we will schedule an

individual telephone call during this week for problem solving with the participant. Finally, we will discuss both short-term and long-term relapse prevention strategies in the third phase.

Pharmacologic Intervention. All participants will receive varenicline (i.e., Chantix™) in conjunction with the behavioral smoking cessation intervention. All participants will receive varenicline 0.5 mg once daily for 3 days, increasing to 0.5 mg twice daily for days 4 to 7, and then to the maintenance dose of 1 mg twice daily for a total of 6 months of treatment.

Booster Weight Management Sessions: Participants randomized to Group 1 and 2 will receive monthly booster weight management sessions, after completing the 6-week behavioral smoking cessation intervention. There will be 5 booster sessions (week 16, 20, 24, 28, and 32) that will focus on problem solving related to weight management. Participants will receive the booster sessions with the same group with whom they received the weight management and smoking cessation interventions, in order to preserve group social support as well as reduce contamination concerns. We decided to focus these booster sessions on problem solving for both Group 1 and 2.

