Our hypotheses include that randomization to the SMALL and LOSS conditions will produce smaller post-cessation weight gain compared to participants in the BIBLIO condition. The main independent variable of interest will be treatment assignment and the outcome will be weight change from baseline to 12-month follow-up. Measures of weight will be obtained at multiple time points to provide feedback, but we will model only the final measure to capture full post-cessation weight gain. Two separate general linear and mixed ANCOVA-like regression models for continuous measures will be utilized, with treatment effect estimated as the distance between the fitted group-specific means at the 12-month data collection visit (SMALL compared to BIBLIO and LOSS compared to BIBLIO), while adjusting for the fitted distance between them at baseline. In addition, we will adjust within the model for demographic factors, baseline weight, and other covariates if needed; however, due to randomization, we do not anticipate significant differences in baseline distributions. We will also test the interactions between treatment assignment and demographic covariates to examine the homogeneity of treatment effects. We will include smoking status within our modeling strategy either as moderator or a confounder. We hypothesize no significant difference in post-cessation weight gain between the SMALL and LOSS conditions. We will compare the two conditions within the scope of the regression models described previously. The main treatment comparison results will be considered significant at $\alpha = .017$ due to three pre-planned contrasts, with all other associations at $\alpha = .05$.

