We hypothesize that participants randomized to the SMALL, LOSS, and BIBLIO conditions will have similar rates of smoking cessation at 12-month assessment. Given that the outcome is binary (i.e., prolonged abstinence; yes or no) and the treatment conditions are nominal, we will use categorical analytical methods. To test the differences in prolonged abstinence between the intervention arms, we will apply χ^2 test and then a multivariate logistic regression model, with BIBLIO selected as the referent group compared to the other conditions. We will estimate the relative odds of a treatment effect on prolonged abstinence while adjusting for baseline demographics, smoking history (e.g., onset of regular smoking, quit attempts, use of tobacco products), process measures and other potential confounders. As such, we can test the associations and estimate effects of additional variables, besides treatment effect.

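### The allocation ratio changes with wave size, but the SAP commits to no wave or allocation-ratio term, leaving both comparisons with BIBLIO open to a small, avoidable bias

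*Protocol*

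**What the plan says.** Protocol section 5 (Study Project Procedures) sets the main ratio: "Participants (n=400) will be randomly assigned in a ratio of 2 (Group 1, n=160): 2 (Group 2, n=160): 1 (Group 3, n=80". The next sentence makes an exception: "when less than 40 participants are recruited for a wave, the biostatistician will more evenly distribute the participants". The replacement ratio is not stated, nor is the number or size of waves.

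For weight change from baseline to 12 months, the SAP says "Two separate general linear and mixed ANCOVA-like regression models for continuous measures will be utilized". On adjustment it says "we will adjust within the model for demographic factors, baseline weight, and other covariates if needed", and then that "due to randomization, we do not anticipate significant differences in baseline distributions". Smoking status is to enter as a moderator or confounder. SMALL-BIBLIO, LOSS-BIBLIO and SMALL-LOSS are each tested at .017.

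For prolonged abstinence, the SAP plans a chi-square test and then a logistic model with BIBLIO as referent. That model adjusts for demographics, smoking history, and "process measures and other potential confounders".

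The SAP does not mention wave, cohort, stratum or allocation ratio anywhere.

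**The concern.** When the allocation ratio differs between strata, randomisation makes the arms comparable within a stratum but not after pooling. Any ratio more even than 2:2:1 raises BIBLIO's share of small waves, so the direction of the imbalance follows from the rule itself. A difference in mean outcome between small and large waves then enters both BIBLIO contrasts with the same sign. If small-wave participants gain more weight, both interventions look better than they are; if they gain less, both look worse. Two of the three main contrasts are affected. SMALL-LOSS is not, as long as those two arms stay equal within each wave.

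The SAP's reliance on randomisation for balance does not allow for this. Its route to extra covariates runs through baseline differences and the comparison of completers with non-completers. A wave effect that arises after baseline need not show up in either.

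**Working it through.** **Figures in the plan.** 400 × (2/5, 2/5, 1/5) = 160/160/80, as stated. 0.05/3 = 0.0167, which rounds to the stated .017. The documents give no SD, effect size or power calculation, so none can be reproduced.

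**Assumptions, not from the documents.** N = 400; residual SD 6 kg (range 5-7); 10-90% of participants in waves under 40; small-wave ratio 1:1:1 or 3:3:2; difference D in mean 12-month weight change between small and large waves of 1, 2 or 3 kg; two-sided test at .017 (critical value 2.387).

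**Formulas.** Let Ns and Nl be the numbers in small and large waves, and let the small-wave fractions be a (each active arm) and b (BIBLIO).
- n_BIB = Ns·b + Nl/5 and n_act = Ns·a + 2Nl/5.
- p_BIB = Ns·b/n_BIB and p_act = Ns·a/n_act; gap = p_BIB − p_act.
- Size of bias = gap × D.
- True SE = SD·√(1/n_BIB + 1/n_act).
- The estimated SE replaces SD² by the arm-size-weighted mean of SD² + D²p(1−p), because an omitted wave effect inflates the residual variance.
- Type I error = P(|X| > 2.387 × estimated SE), with X normal, mean = bias, SD = true SE.

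**Worked case: half in small waves, 1:1:1, D = 2 kg, SD 6 kg.**
- n_BIB = 66.7 + 40 = 106.7; n_act = 66.7 + 80 = 146.7.
- p_BIB = 66.7/106.7 = 0.625; p_act = 66.7/146.7 = 0.455; gap = 0.170.
- Bias = 0.170 × 2 = 0.34 kg.
- √(1/106.7 + 1/146.7) = 0.1273, so the true SE is 0.764 kg. The inflated variance is 36.98, so the estimated SE is 0.774 kg.
- Rejection limit = 2.387 × 0.774 = 1.847 kg. Upper tail beyond (1.847 − 0.341)/0.764 = 1.97 plus lower tail beyond (1.847 + 0.341)/0.764 = 2.87 gives .026.

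**Over the whole range.** The gap is 5.5-17.2 percentage points under 1:1:1 and 2.4-7.2 under 3:3:2. Per 1 kg of wave difference the bias is therefore 0.06-0.17 kg (at most 0.22 SE) or 0.02-0.07 kg (at most 0.09 SE).

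| D | 1:1:1, SD 6: maximum type I error | 1:1:1: maximum at SD 7 to SD 5 | 3:3:2, SD 6: maximum |
|---|---|---|---|
| 1 kg | .0194 | .0188 to .0204 | .0171 |
| 2 kg | .0264 | .0240 to .0305 | .0172 |
| 3 kg | .0379 | .0325 to .0467 | .0175 |

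With only 10% of the sample in small waves (1:1:1, SD 6 kg), type I error is at most .020 even at 3 kg. Against the 4.7 kg mean 12-month gain quoted in protocol section 1, 2 kg is 43% and 3 kg is 64%. Those two rows are stress cases.

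**Simulation check.** There were 100,000 replicates with small/large cells of 67/40 for BIBLIO, 66/80 for SMALL and 67/80 for LOSS. With no stratum term, the BIBLIO contrasts were biased by −0.17, −0.34 and −0.52 kg, with type I error .019, .026 and .039 at 1, 2 and 3 kg. SMALL-LOSS bias was within about 0.01 kg. With the stratum term, every contrast was within 0.01 kg of zero and type I error was .016-.017.

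**The case against.** The strongest objection is that harm needs two things the documents do not show: waves on both sides of 40, and outcomes that differ by wave type. That stands, and it is the main reason for the low rating.

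A second objection is that group delivery is weak evidence for a wave effect. The protocol says "they will receive the smoking cessation intervention with the same group with whom they received the weight management intervention", partly to limit contamination, which suggests groups formed within an arm. That points to clustering within arms rather than a shift common to all arms in a small wave. This is fair: group delivery makes a shared wave effect possible but does not establish or quantify one.

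Third, the SAP wording leaves room for a wave term, and the planned baseline covariates would absorb whatever part of a wave difference they explain. Both points stand. The figures are therefore upper bounds if D is read as a raw wave difference. But permission is not commitment, and an undefined need for covariates could be judged after the data are seen.

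Fourth, the SAP is dated January 2019 and the protocol November 2020. The wave rule may postdate the SAP; the documents do not say. That might explain the gap but does not close it.

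The more even split is not itself at fault. At an assumed standardised effect of 0.4, power for a BIBLIO contrast is 0.703 with 160 v 80 and 0.775 with half the sample at 1:1:1.

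**Conclusion.** The concern holds as a minor pre-specification gap. Three points are certain from the text or the rule: the ratio depends on wave size, the ratio below 40 is unstated, and no wave or ratio term is committed to. The direction of the imbalance follows.

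The size is conditional on the assumptions above. For a 1 kg wave difference it is slight: at most 0.17 kg of bias and type I error of about .019 against .017. It becomes visible only when 1:1:1, a mid-range small-wave share and a 2-3 kg wave difference coincide. Under 3:3:2 it is negligible. For abstinence the same gap exists, but it was not quantified, is likely to matter less, and is a secondary reason only.

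**What to change.** 1. State one allocation ratio in advance for all waves under 40, and record the ratio used in each wave.
2. Pre-specify the allocation-ratio stratum, with one level per ratio used, as a covariate in the 12-month weight model and in the abstinence logistic model.
3. Optionally, add a Cochran-Mantel-Haenszel test stratified the same way beside the planned chi-square for abstinence.

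If randomisation is already complete, the ratios used can still be documented and the term added, declared as a late specification.

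The cost is SAP wording and a short record. A two-level term raises the standard error of a BIBLIO contrast by at most about 0.9% in a three-arm model or 1.5% in separate two-arm models under 1:1:1. Under 3:3:2 the figures are 0.15% and 0.24%. For example, in the two-arm model with half the sample in small waves at 1:1:1, SE/SD goes from 0.1273 to 0.1291. In return, the bias from the varying ratio is removed under an additive model.

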- Participants must have a self-reported BMI of 22 kg/m² or greater, as it would not be recommended to have those who are underweight or the lower end of the normal BMI range attempt a 5% weight loss (if assigned to Group 2)
- Participants must have access to a telephone and daily access to email. If using a cell phone, participants must be willing to use their cell phone minutes for weekly phone interventions as well as for some or all of the remote data collection visits
- All women of childbearing age must have a negative pregnancy test and must agree to use contraception during participation in the study
- Participants must also be willing to be randomized to the study conditions and wait eight weeks prior to beginning smoking cessation (during which they will participate in the weight management intervention to which they are assigned)
- Participants must have blood pressure that is < 150/95 mmHg and heart rates of >40 beats per minute and <120 beats per minute (according to their health care provider)
- Participants must be able to exercise for at least 10 minutes
- Participants must also have the ability to understand the consent process in English

Exclusion Criteria:

[figure not shown]
- Have a known contraindication, allergy or hypersensitivity to Varenicline

- Are currently (in the previous 30 days) participating in other behavioral or pharmacologic weight or smoking cessation interventions
- Have used an investigational drug within the last 30 days
- Have current suicidal thoughts or have a lifetime history of a suicide attempt as defined by the Columbia-Suicide Severity Rating Scale (C-SSRS) (76)
- Have a self-reported history of psychosis, bipolar disorder or anorexia nervosa
- Self-report current alcohol abuse or illicit substance use
- Have kidney disease or liver disease; HIV; have unstable cardiovascular conditions, or have history of cancer in the last 5 years
- Taking medications that impact weight (see list)
- History of gastric bypass, stomach stapling, banding or other weight loss surgery
- Lost \geq 10 pounds in the last 6 months
- Have another member of their household already participating in this study
- Pregnancy within the last 6 months, breastfeeding or planning to become pregnant during the study follow-up time (12 months)
- Weight limit of 385 pounds

4. Research Design

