As seen in [Figure 1](#), we will randomize up to 400 participants to 3 conditions: a) a weight stability intervention (Group 1); b) a weight loss intervention (Group 2); and c) a minimal intervention condition (Group 3). All 3 conditions receive a highly efficacious smoking cessation program and 6 months of varenicline pharmacotherapy (ChantixTM). Those participants randomized to Group 1 & 2 will receive monthly booster weight management sessions, after completing the smoking cessation intervention.

Figure 1. Study Design

5. Study Project Procedures

Intervention Trial Screening and Baseline Procedures. Individuals who meet the phone screening eligibility criteria will be invited to schedule a remote Screening Visit (via phone) and the participant's e-signature will be obtained via DocuSign. If the self-reporting questionnaires cannot be done via phone they may be emailed or mailed (along with an addressed and stamped envelope) to the participant for completion. If the participant does not want to use DocuSign, the consent form may be mailed to prospective participants with a return envelope and staff will conduct the consent process over the phone prior to the participant signing the consent form and mailing it back. If consent is done in this way, staff will wait to complete the rest of the remote Screening Visit until receiving the signed consent form. If appropriate, a pregnancy test will be mailed to the participant along with instructions and staff will obtain their self-reported pregnancy test result via a follow-up call. If the participant is willing, they may email a picture of their test result. Participants will receive information regarding how to complete 3 behavioral run-in items, as an indicator of their motivation to participate in the trial over the next 12 months.

Behavioral run-in tasks include:

1. A daily diet and exercise journal (3 days)
2. Liking the study on Facebook (encouraged, but not required)
3. Obtaining physician permission to participate

Participants will complete another remote study visit ("Baseline") to evaluate behavioral run-in performance and determine randomization eligibility. A BodyTrace e-scale will be mailed to the participant and they will be asked to weigh to confirm eligibility. If participants meet eligibility requirements, they may begin the randomization process.

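### The visible protocol describes one pregnancy test, about 9 to 11 weeks before varenicline is first supplied, and no check at supply or during the 6 months of drug

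*Protocol*

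**What the plan says.** **Entry.** Protocol section 3, Inclusion Criteria: "All women of childbearing age must have a negative pregnancy test and must agree to use contraception during participation in the study". The Exclusion Criteria also bar recent pregnancy, breastfeeding, and any plan to conceive within the 12 months of follow-up.

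**The test.** Protocol section 5, screening and baseline procedures: "If appropriate, a pregnancy test will be mailed to the participant along with instructions", after which "staff will obtain their self-reported pregnancy test result via a follow-up call". Sending a photograph of the result is optional. No repeat test is mentioned.

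**The drug.** Protocol section 5, Behavioral Smoking Cessation Intervention: "Participants will transition to the smoking cessation intervention at week 9". The same paragraph continues: "First, we will prepare participants for the quitting process, including providing varenicline at the first session". Under Pharmacologic Intervention, "All participants will receive varenicline 0.5 mg once daily for 3 days", with the dose raised over the first week and "then to the maintenance dose of 1 mg twice daily for a total of 6 months of treatment". No condition is attached to first or continued supply.

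**Safety review.** Protocol section 5, Safety Measures, plans questions on adverse events and suicidality at the data collection visits and at monthly calls about the medication. The study physician is brought in for deteriorating depression, suicidal ideation or an adverse event. Pregnancy appears in neither list. The SAP does not mention pregnancy.

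**The concern.** The design puts a waiting period between the pregnancy test and the drug. Participants are screened, randomized, and then spend eight weeks in a weight programme before the cessation phase starts. The one described test falls when no drug is being given, and nothing comparable is described when the drug is first handed over or during the months that it is taken.

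A woman who conceives during the wait or while on treatment would, on the visible text, continue to be supplied unless the pregnancy came to light in some other way. The stake is participant safety and a coherent rule for supply. The point has no bearing on the error rate, the power or the 12-month weight comparison.

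**Working it through.** The documents state no figure for this gap, so there is none to reproduce. The check is date arithmetic followed by a comparison of sections.

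**Inputs**
- Table 1 prints week labels -2, -1 and 0 after the column names Screening, Baseline and Randomization. The natural reading pairs them in that order. The header is broken in the extract, so this pairing is an assumption.
- First supply is at week 9 (section 5, Behavioral Smoking Cessation Intervention).
- Duration of drug is 6 months, about 26 weeks (section 5, Pharmacologic Intervention).

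**Step 1: test to first supply** (week 9 minus week of test)
- Test at screening, week -2: 9 - (-2) = 11 weeks.
- Result in hand only by baseline, week -1: 9 - (-1) = 10 weeks.
- Counted from randomization, week 0: 9 - 0 = 9 weeks.

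The text sets no maximum interval from test to randomization, so the range of 9 to 11 weeks rests on the table labels.

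**Step 2: test to end of drug**
- End of drug: 9 + 26 = week 35. The 8-month visit, placed after varenicline is finished, falls at 8 × 52/12 = 34.7 weeks, which agrees.
- Span without a described check: 35 - 0 = 35 weeks to 35 - (-2) = 37 weeks.

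**Step 3: is there already a contact just before supply?**
- The 2-month visit falls at week 8 by phase length, or at 2 × 52/12 = 8.7 weeks by the calendar. That leaves 9 - 8 = 1 week down to 9 - 8.7 = 0.3 weeks before week 9. A question can be asked there at no extra contact. A kit mailed only after that visit may arrive after the first session.

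**Step 4: comparison with another entry exclusion**
- Suicidality: excluded at entry, asked about again at visits and monthly calls, and referred to the study physician.
- Pregnancy: excluded at entry, with no repeat question or test described and no named referral.

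**Step 5: do the other safeguards detect a pregnancy?**
- Contraception throughout participation and the exclusion of planned pregnancy reduce how often one occurs. Neither reveals one that has occurred.
- Physician permission is obtained once, as a run-in task before randomization.
- Adverse-event questions could bring a recognised pregnancy to light, but the text does not name it as reportable.

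Table 1 shows a single mark in the pregnancy-test row, but marks elsewhere in the table appear displaced or lost. The conclusion rests on the prose, which describes no later check.

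**The case against.** The strongest reply is that the plan made a deliberate choice: one test at entry, contraception for the whole of participation, exclusion of anyone planning a pregnancy, and regular contact with physician back-up. No commitment is broken. This is right as far as it goes. A reader might infer that the protocol fails its own entry condition when it hands out the drug. The documents do not support that: the negative test is an entry criterion, it is met at entry, and nothing makes it a condition of supply.

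A second reply is that the consent pages are not available and could tell women to report a pregnancy or stop the drug. That also stands, and it limits the finding to what the visible protocol describes.

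Third, the documents do not say whether pregnancy is excluded because of the drug or because it would disturb the weight outcome, and they give no expected number of pregnancies. A reader might infer a specific drug harm or a bias in the weight comparison. Neither can be drawn from these documents and neither is claimed. What survives is narrower. The protocol treats pregnancy as a reason not to enter a trial in which everyone receives this drug, and then describes no way of noticing one once the drug begins.

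Fourth, a fixed figure of 11 weeks would be too precise, given the state of Table 1. The range of 9 to 11 weeks meets that objection. Nor should the point be widened to new medical contraindications in general, which the adverse-event review largely covers.

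**Conclusion.** The point holds as a gap in safety monitoring that is worth closing. In the visible protocol, the only described pregnancy check is one mailed, self-reported test around screening. It comes about 9 to 11 weeks before varenicline is first supplied, and nothing further is described for the 6 months on drug, giving about 35 to 37 weeks in all.

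This rests on three assumptions: that the Table 1 labels -2, -1 and 0 belong to screening, baseline and randomization; that 6 months is about 26 weeks; and that the unavailable consent pages do not already contain a reporting and supply rule. The number of women affected is unknown and is not estimated. Confidence is medium, mainly because of the consent pages.

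**What to change.** 1. At the existing 2-month visit, before first supply, and at each monthly medication call, ask women of childbearing age about pregnancy or a missed period.
2. If the answer is positive or uncertain, send the mailed self-test already described for screening and refer the participant to the study physician. Mailing kits during follow-up is already planned for cotinine, so the route exists.
3. Add pregnancy to the events in Safety Measures that go to the study physician.
4. In the Behavioral Smoking Cessation and Pharmacologic Intervention paragraphs, make first and continued supply subject to that review. The clinical action is for the physician to set.
5. Keep affected women in follow-up and in the intention-to-treat analysis, as the SAP already requires for all randomized cases, and record the pregnancy.

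If the consent form already has such a rule, carry it into the protocol. A question alone will miss a pregnancy that the woman has not recognised. Mailing a kit to every such woman before week 9 would address that, but it is an added procedure and this fix does not depend on it.

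The cost is some protocol wording, one question at contacts already planned, and an occasional kit. The downside is that a few participants may start varenicline later than the group with whom they attend sessions, or not at all.
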